##### **4.5.3.3.1 Electrocardiogram values over time**

Twelve-lead ECG variables and changes from Baseline will be summarized using descriptive statistics by BRV formulation (tablet or dry syrup) at each scheduled time point. [All]

The following cut-points in QTcF (raw data and change from Baseline) will be summarized categorically by BRV formulation (tablet or dry syrup) (number and percentage of participants) and timepoint.

Raw QTcF data:

- $< 450$  msec
- $\geq 450$  msec to  $< 480$  msec
- $\geq 480$  msec to  $< 500$  msec
- $\geq 500$  msec

Change from Baseline QTcF:

- <30msec
- $\geq$ 30msec to <60msec
- $\geq$ 60msec

[All]

Electrocardiogram findings will be listed for the RS. [All]

#### **4.5.3.3.2 Individual participant changes of electrocardiograms values**

By-participant listings of all twelve-lead ECG variables, and change from Baseline will be presented by treatment sequence, period, visit, BRV formulation (tablet or dry syrup) and time point for the RS. [All]

#### **4.5.3.4 Other safety endpoint(s)**

By-participant listings of physical examination data will be presented by treatment sequence, and time point and BRV formulation (tablet or dry syrup) for the RS. [All]

By-participant listings of impact of COVID-19 will be presented for the ES. [All]

### **4.6 Other analyses**

#### **4.6.1 Other endpoints and/or parameters**

The other PK endpoints are defined as follows:

- Measured concentration at the end of a dosing interval at steady state,  $C_{trough}$
- Apparent total body clearance at steady state,  $CL_{ss}/F$
- Time of maximum plasma concentration at steady state,  $t_{max,ss}$
- Time of the last measurable concentration,  $t_{last}$
- Area under the curve from time zero (pre-dose) to the last quantifiable concentration,  $AUC_{last}$
- Apparent terminal elimination half-life,  $t_{1/2}$
- Terminal elimination rate constant,  $\lambda_z$
- Percentage of  $AUC_{tau}$  obtained by extrapolation beyond  $t_{last}$ ,  $\%AUC_{ex}$

##### **4.6.1.1 Pharmacokinetics**

All pharmacokinetic analyses will be performed using the PKS unless otherwise specified.

#### 4.6.1.1.1 Plasma concentration-time profiles

For each Dosing Period, blood samples for PK analysis will be collected on Day 1 (before the morning and evening doses [0 and 12hr]), Day 2 (before the morning and evening doses [24 and 36hr]), and Day 3 (predose [48hr] and 10min, 15min, 20min, 30min, 45min, 60min, 75min, 90min, 2hr, 6hr, 9hr, and 12hr postdose). Allowable deviations from these scheduled PK sampling times are provided in Table 8-1 of the protocol. Individual concentration-time data will be listed for the SS by treatment sequence. [All]

Concentration listings will include nominal PK sampling time, actual sampling times relative to dose administration, deviation from nominal time, and concentrations, day, dosing period and sequence, formulation (tablet or dry syrup).

Plasma concentration data will be listed and summarized with the descriptive statistics by BRV formulation (tablet or dry syrup) and scheduled time for the PKS. [All]

Descriptive statistics will include number of study participants (N), number of available observations (n), mean, standard deviation, median, minimum, and maximum, geometric mean, geometric coefficient of variation (CV), and 95% confidence interval (CI) for the geometric mean.

The geoCV will be calculated as  $geoCV(\%) = 100 \times \sqrt{\exp\{(lnSD)^2\}} - 1$ , where  $lnSD$  is the standard deviation of the log transformed values.

Graphical displays of geometric mean concentrations with its corresponding 95% CI (linear scale and semi-logarithmic scale) on Day 1 to Day 3 and zoomed geometric mean concentrations between 0 and 6 hr on Day 3 will also be presented by BRV formulation (tablet or dry syrup) and scheduled time on semi-logarithmic and linear scales for the PKS. [IA-DMC, All]

Graphical displays of individual plasma concentrations by actual time will be presented on semi-logarithmic and linear scales.

Plasma concentrations will be displayed superimposed in a single plot for both formulations for the PKS. [All]

Spaghetti plots will be presented on Day 3 up to 12 h post-dose separately for BRV formulation, with profiles for all participants superimposed on the same graph for the PKS. [All]

Refer to [Appendix 12](#) (Section 6.12) for standard reporting procedures of individual values and descriptive statistics for plasma concentration data in listings, tables, and figures.

#### 4.6.1.1.2 Derivation of primary/ other pharmacokinetic variables and descriptive summaries

Pharmacokinetic parameters will be calculated by non-compartmental analysis methods from the concentration-time data using Phoenix® WinNonlin® (Version 8.2 or higher).

Actual sampling times will be used for deriving the PK parameters. Pharmacokinetic parameters will be estimated according to the guidelines presented in [Appendix 13](#), Section 6.13.

$C_{max,ss}$ ,  $AUC_{tau}$ ,  $CL_{ss}/F$ ,  $t_{max,ss}$  and  $C_{trough}$  will be listed by participant and summarized with descriptive statistics by BRV formulation (tablet or dry syrup) for the PKS. [IA-DMC, All]

For individual  $C_{max,ss}$  and  $AUC_{tau}$ , ratio of Test (dry syrup) versus Reference (tablet) will be listed by participant and summarized with descriptive statistics for the PKS. [All]

The ratios between the  $C_{trough}$  after the last dose on Day 3 and the pre-dose concentration before each dose with the exclusion of morning dose on Day 1 ( $R_{trough}$ ) will be listed by participant and summarized with descriptive statistics for the PKS. [All]

For  $t_{max,ss}$ , a distribution-free 90% CI using Hodges-Lehmann's method will be calculated for the median differences (location shift) between each Test (dry syrup) and the Reference (tablet). Median and the corresponding 90% CI for each treatment (tablet or dry syrup) will be provided using cumulative binomial probability. If the exact Hodges-Lehmann confidence limits cannot be calculated, asymmetric limits will be derived instead of symmetric limits. [All]

In addition, all individual PK parameters will be listed by formulation (tablet or dry syrup) for the SS. [All]

The following descriptive statistics will be calculated: mean, SD, geometric mean, geometric coefficient of variation (CV), minimum, median and maximum and 95% confidence interval (CI) for the geometric mean. The only exception is  $t_{max,ss}$ , for which only median, minimum, and maximum will be reported.

Ping pong plots for individual data in the PK parameters ( $C_{max,ss}$  and  $AUC_{tau}$ ) will also be displayed for the PKS. [All]

Refer to [Appendix 12](#) (Section 6.12.2) for standard reporting procedures of individual values and descriptive statistics for PK parameters in listings and tables.

#### **4.6.1.2 Pharmacodynamics**

Not applicable.

#### **4.6.1.3 Population pharmacokinetics**

Not applicable.

#### **4.6.1.4 Immunogenicity**

Not applicable.

#### **4.6.1.5 Genomics**

Not applicable.

#### **4.6.1.6 Biomarkers**

Not applicable.

#### **4.6.1.7 Pregnancy outcomes**

Not applicable.

#### **4.6.1.8 Health care utilization related endpoints**

Not applicable.

#### **4.6.1.9 Health technology assessment related endpoints**

Not applicable.

### **4.6.2 Subgroup analyses**

Not applicable.

### **4.7 Interim analyses**

The study may consist of 2 cohorts. A formal interim analysis is planned at the end of Cohort 1, once approximately 60 evaluable participants have completed the study. If bioequivalence or futility is not established in the interim analysis, the final analysis is planned at the end of Cohort 2, once all participants (approximately 90) have completed the study (See Section 9.8 of the protocol). The interim analysis, based on a group sequential design, will be an unblinded analysis performed by an internal statistical team independent from the study team and will focus on the analysis for primary PK parameters  $C_{max,ss}$  and  $AUC_{tau}$ . The results will be reviewed by an internal DMC, which is independent from the study team, and the following decisions will be made:

1. Early stopping of the study due to demonstrating bioequivalence at the end of Cohort 1:  
The study will be stopped early, after Cohort 1, if bioequivalence between the Test (dry syrup) and Reference (tablet) formulations is established for  $C_{max,ss}$  and  $AUC_{tau}$  (Section 9.3.1 of the protocol).
2. Early stopping of the study for futility at the end of Cohort 1:  
The study will be stopped early, after Cohort 1, in the event that bioequivalence is not established and the 1-sided (upper) 95% CI of the adjusted GMR (Test/Reference) is less than 0.8700 for  $C_{max,ss}$ . This corresponds to the GMR of this study being markedly lower than that of single-dose bioequivalence study (EP0110).
3. Continuing to Cohort 2:  
If bioequivalence or futility is not established, the study will continue to Cohort 2, and the remaining approximately 30 participants will be randomized.

### **4.8 Changes to protocol-planned analyses**

The following evaluation was added in the protocol amendment dated 14 December 2023.

In the case that the CIs for  $C_{max,ss}$  and  $AUC_{tau}$  are not contained in the range of 0.80 to 1.25, bioequivalence can still be concluded if the following criteria are met:

1) The point estimate of the adjusted GMR (Test/Reference) for  $C_{max,ss}$  and  $AUC_{tau}$  are contained in the range of 0.90 to 1.11.

2) In vitro dissolution rates of Test (dry syrup) and Reference (tablet) formulations are available and are deemed similar according to [the Japanese bioequivalence guideline](#) (PSEHB/PED Notification No. 0319-1, 2020).

#### **4.9 Data Monitoring Committee (DMC) or other review board**

As described in Section 9.7 of the protocol, a formal interim analysis is planned at the end of Cohort 1 once approximately 60 evaluable participants have completed the study. The results will be reviewed by an internal DMC, which is independent from the study team. The DMC will make 1 of the following decisions:

- 1) Early stopping of the study if the study demonstrates bioequivalence at the end of Cohort 1.
- 2) Early stopping of the study if the study is futile at the end of Cohort 1.
- 3) Continuing the study to Cohort 2.

Details of the DMC will be provided in the DMC Charters.

### **5 SAMPLE SIZE DETERMINATION**

A total of up to approximately 90 participants are planned to be evaluable for the primary endpoint.

As detailed in Section 9.7 of the protocol, this study may consist of 2 cohorts, with a formal interim analysis once Cohort 1 has completed both Dosing Periods.

The BRV single-dose bioequivalence study (EP0110) between tablet (Reference) and dry syrup (Test) provided estimates of the GMR (Test/Reference) of 0.8700 for  $C_{max}$  and 0.9890 for  $AUC_{(0-t)}$  and the intraparticipant variability (CV%) of 21.9% for  $C_{max}$  and 2.7% for  $AUC_{(0-t)}$  ([Table 5-1](#)). The BRV multiple-dose PK simulation results based on the EP0110 study data provided estimates of the GMR of 0.9054 for  $C_{max,ss}$  and 0.9893 for  $AUC_{tau}$  and the intraparticipant variability (CV%) of 15.3% for  $C_{max,ss}$  and 2.7% for  $AUC_{tau}$ .

**Table 5-1: EP0110 and simulation results of relative bioavailability of BRV tablet formulation vs dry syrup formulation**

Parameter	Statistic	EP0110	MD Simulation
$C_{max}$ ( $\mu\text{g/mL}$ ) a	GMR of dry syrup/tablet (Intraparticipant CV%)	0.8700 (21.9)	0.9054 (15.3)
$AUC$ ( $\text{h}^*\mu\text{g/mL}$ ) b	GMR of dry syrup/tablet (Intraparticipant CV%)	0.9890 (2.7)	0.9893 (2.7)

AUC=area under the curve;  $AUC_{(0-t)}$ =area under the curve from time 0 to the time of the last quantifiable concentration;  $AUC_{\tau}$ =area under the curve during a dosage interval at steady state; BRV=brivaracetam;  $C_{max}$ =maximum plasma concentration;  $C_{max,ss}$ =maximum plasma concentration at steady state; CV=coefficient of variation; GMR=geometric mean ratio; MD=multiple-dose

a The  $C_{max,ss}$  was used for MD simulation results, estimated based upon the EP0110 study data.

b The  $AUC_{(0-t)}$  was used for EP0110. The  $AUC_{\tau}$  was used for MD simulation results, based upon the EP0110 study data.

In the event that EP0231 will have results similar to those observed in EP0110 without any improvement by the multiple-dose study design, 116 participants will be needed to provide a power of 90% with a fixed design (no interim analysis). However, because this study is conducted as a multiple-dose study, it is expected that the PK profile variability will be smaller. It is assumed that both the GMR and intraparticipant SD will show improvement (higher GMR and smaller intraparticipant SD) compared with the single-dose study (EP0110), closer to those shown in the multiple-dose PK simulation results. The study assumptions for GMR and intraparticipant CV% (for  $C_{max}$ ) are based on the approximate middle values of those seen in EP0110 and the multiple-dose PK simulations based on the EP0110 study data, assuming a GMR of 0.89 and intraparticipant SD of 0.183 (corresponding to a CV% of 18.5%).

In the group sequential design for this study, an interim analysis will be performed for bioequivalence or futility after approximately 60 evaluable participants, which is at 90% power for bioequivalence based on the CIs of the adjusted GMR (Test/Reference) with the study assumptions. Should the assumption regarding variability and GMR not hold, with the study consequently not being stopped for demonstrating bioequivalence or futility at the interim analysis, this allows the opportunity to enroll a further approximately 30 participants and assess bioequivalence after approximately 90 evaluable participants. While maintaining the two 1-sided significance level of 0.05, this should be sufficient to state that the true GMR is in the range of 0.80 to 1.25. The two 1-sided significance levels currently used are 0.03817 for the interim analysis and 0.02704 for the final analysis according to the Lan-DeMets alpha spending function approximating a Pocock boundary, assuming 60 evaluable participants in Cohort 1 and 30 evaluable participants in Cohort 2 as the number of participants to be included in the analyses. A total of 90 evaluable participants will provide an overall power of >75% even if the GMR and intraparticipant CV% remain as observed in EP0110.

The probability of study stopping for demonstrating bioequivalence for Cohort 1 (power at Cohort 1), futility at Cohort 1, and proceeding to Cohort 2 are approximately 91%, approximately 1%, and approximately 8%, respectively. If the study continues to Cohort 2, the bioequivalence will be assessed after completing Cohort 2.

In order to ensure a total of up to approximately 90 evaluable participants for the primary endpoints, assuming a rate of dropout and non evaluable participants of approximately 5%, 64 participants for Cohort 1, 32 participants for Cohort 2, and up to 96 participants in total are estimated to be randomized in the study.

## 6 APPENDIX: SUPPORTING DOCUMENTATION

### 6.1 Appendix 1: List of Abbreviations

#### List of Abbreviations

AE	Adverse Event
ALP	Alkaline Phosphatase
ALT	Alanine Aminotransferase
AST	Aspartate Aminotransferase
ATC	Anatomical Therapeutic Chemical
AUC	Area under the Curve
AUC last	Area under the Curve from Time Zero (pre-dose) to the Last Quantifiable Concentration
AUC tau	Area under the Curve during a dosage interval at steady state
%AUC ex	Percentage of AUC tau Obtained by Extrapolation from Tlast to Time tau
BE	Bioequivalence
BLQ	Below the Limit of Quantification
BMI	Body Mass Index
BRV	Brivaracetam
CI	Confidence Interval
CL ss /F	Apparent Total Body Clearance at Steady State
C max,ss	Maximum Plasma Concentration at Steady State
COVID-19	Coronavirus Disease 2019
C trough	Measured Concentration at the End of a Dosing Interval at Steady State
CSR	Clinical Study Report
CV	Coefficient of Variation
DBP	Diastolic Blood Pressure

**List of Abbreviations**

DEM	Data Evaluation Meeting
DILI	Drug Induced Liver Injury
DMC	Data Monitoring Committee
ECG	Electrocardiogram
eCRF	Electronic Case Report Form
ES	Enrolled Set
FA	Final Analyses
geoCV	Geometric Coefficient of Variation
GMR	Geometric Mean Ratio
IA	Interim Analyses
IMP	Investigational Medicinal Product
IPD	Important Protocol Deviation
$\lambda_z$	Terminal Elimination Rate Constant
LLoQ	Lower Limit of Quantification
Max	Maximum
MD	Multiple Dose
MedDRA	Medical Dictionary for Regulatory Activities
Min	Minimum
PDILI	Potential Drug Induced Liver Injury
PED	Pharmaceutical Evaluation Division
PT	Preferred Term
PK	Pharmacokinetic
PKS	Pharmacokinetic Set
PSEHB	Pharmaceutical Safety Environment Health Bureau
QTc	QT Interval Corrected for Heart Rate
QTcF	QTc Using Fridericia's Correction
REML	Restricted Maximum Likelihood
RS	Randomized Set
R trough	Ratio between the C trough after the last dose on Day 3 and the pre-dose concentration before each dose with the exclusion of morning dose on Day 1
SAE	Serious Adverse Event
SAP	Statistical Analysis Plan
SBP	Systolic Blood Pressure

### List of Abbreviations

SD	Standard Deviation
SFU	Safety Follow-Up
SOC	System Organ Class
SS	Safety Set
TEAE	Treatment-Emergent Adverse Event
TFLs	Tables, Figures and Listings
$t_{1/2}$	Apparent Terminal Elimination Half-life
$t_{last}$	Time of the Last Measurable Concentration
$t_{max,ss}$	Time of $C_{max,ss}$
tobs	Actual Sampling Time at Planned Timepoint tau
ULN	Upper Limit of Normal
WHO	World Health Organization

## 6.2 Appendix 2: Coding dictionaries

Medical history and adverse events (AEs) will be coded using the Medical Dictionary for Regulatory Activities (MedDRA®), using the MedDRA version 18.1. Medications will be coded using the World Health Organization Drug (WHO-Drug) Sep 2017. Medical procedures will not be coded.

## 6.3 Appendix 3: Participant disposition

Participant screening and primary reason for screen failure will be summarized using the ES. The summary will include the following:

- Number of participants screened
- Number and proportion of participants with screen failures
- Number and proportion of screen failures by primary reason for screen failure

[All]

Disposition of participants will be summarized using the ES. [All]

The number and percentage of participants in each analysis set by BRV formulation (tablet or dry syrup) will be calculated based on the RS. [IA-DMC, All]

Participants who have started the study, completed the study and discontinued the study will be summarized using the RS by treatment sequence. The summary will include the following:

- Number of and proportion of participants who have started the study
- Number of and proportion of participants who have discontinued the study
- Number of and proportion of participants who have completed the study.
- Number of and proportion of participants who have discontinued the study by primary reason.

Participants that started the study are defined as participants that were randomized and dosed.

Participants completing the study are those participants completing all Treatment Periods of the study as well as the SFU assessment. [IA-DMC, All]

By-participant listings of participant disposition will be provided by treatment sequence for ES, and will include the following:

- Study termination/completion status
- Date of informed consent
- Date of randomization
- Date and time of the first and the last IMP administration
- Date of premature study termination for successfully screened participants dropping out of the study
- Date of screen failure for screen failure participants
- Treatment (Period) at discontinuation
- Primary reason for premature study termination, as applicable
- Primary reason for screen failure, as applicable.

[All]

By-participant listings of visit dates will be presented by treatment sequence using the RS. [All]  
By-participant listings of participant who did not meet study eligibility criteria will be presented overall using the ES. [All]

By-participant listings of participant inclusion in each analysis set will be presented overall using the ES. [All]

By-participant listings of participant excluded from each analysis set will be presented by treatment sequence including the reasons for exclusion; the listing will be based on all subjects in the RS. [All]

## **6.4 Appendix 4: Baseline characteristics and demographics**

Demographic variables including year of birth, age, gender (Male), race (Asian), ethnicity (not Hispanic or Latino), height (cm), body weight (kg), and body mass index (BMI: kg/m^2) will be listed by treatment sequence for all participants in the ES. Age will be used as recorded on the electronic case report form (eCRF) and will not be recalculated.

Demographic and the other baseline characteristic variables at Screening will be summarized by BRV formulation (tablet or dry syrup) and overall based on the SS.

The continuous variables will be summarized using descriptive statistics, and the categorical variables will be summarized using frequency counts and percentages.

Age will be summarized in both continuous and categorized (as per clinicaltrials.gov requirements) format.

For the clinicaltrials.gov reporting, the age categories will include:

- $\leq 18$  years
- 19 to  $< 65$  years
- $\geq 65$  years

[All]

Lifestyle data will be summarized by BRV formulation for the SS. [All]  
By-participant listings of lifestyle data will be provided by treatment sequence for the RS. [All]

## 6.5 Appendix 5: Protocol deviations

Important protocol deviations (IPDs) will be summarized by treatment sequence, and overall using the RS as well as participants from the PKS. The summary will include the following:

- Number and percentage of participants with no IPDs
- Number and percentage of participants with at least one IPD
- Number and percentage of participants by type of protocol deviation

[IA-DMC, All]

By-participant listings of IPDs as identified in the Data Cleaning Meeting will be provided by treatment sequence, period, BRV formulation (tablet or dry syrup) using the RS.

This will include deviation type, deviation description, and whether the deviation led to exclusion from any analysis set. [All]

Protocol deviations (e.g., missing assessments or visits) related to COVID-19 will be listed separately. [All]

## 6.6 Appendix 6: Medical /surgical history /concomitant medical procedures

By-participant listings of medical history, surgical /procedure history will be provided by treatment sequence for the RS. Medical history will include MedDRA SOC and PT, reported condition, start date and stop date (or status ongoing, as applicable). [All]

A glossary of medical histories including reported term, SOC and PT will also be presented for the RS. [All]

By-participant listings of concomitant medical procedures will be provided by treatment sequence for RS. [All]

Hepatic event supplemental medical history will be listed for the RS. [All]

## 6.7 Appendix 7: Prior / concomitant medications

If a participant takes a medication before the study medication administration, this medication will be categorized as 'prior medication'. This includes medications that started prior to study medication administration and continued after.

Medication not stopped before the date of study medication administration will be classified as 'concomitant medication'. Medication will also be labeled as 'concomitant medication' when the start date is between the date (including the date) of study medication administration and the date of the participant's last study visit.

From the definitions above, any medication that started prior to dosing and continued after dosing will be classified as both prior and concomitant.

Prior and concomitant medications will be listed by treatment sequence and participant for participants in the RS and will include the reported term, the anatomical therapeutic chemical

(ATC) subgroup (level 1 and 3), preferred term, dose and dose unit, frequency, formulation, indication, prior or concomitant classification flag, start and stop dates (including relative day calculated as described in [Section 4.1.1.1](#)), duration (unit: day, calculated as stop date – start date + 1) and BRV formulation assigned to. [All]

A glossary of medication terms including reported term, preferred term, and ATC levels 1 and 3 will also be presented. [All]

Prior and concomitant medications will be summarized separately for the SS by treatment sequence and overall, ATC code (level 1 and 3), and preferred term, including the number and percentage of subjects receiving each medication as categorized by the ATC subgroup or preferred term. The denominator for percentages will be the number of subjects in the SS for each treatment sequence. [All]

In the case of missing dates, the classification of medications as prior or concomitant will be performed after imputation of dates as described below. Imputations of missing dates will be performed prior to calculation of relative days.

The following rules are applied to impute partial start dates for medications:

- If only the month and year are specified and the month and year of first IMP dose is not the same as the month and year of the start date, then use the 1st of the month.
- If only the month and year are specified and the month and year of first IMP dose is the same as the month and year of the start date, then use the date/time of first IMP dose.
- If only the year is specified, and the year of first IMP dose is not the same as the year of the start date, then use January 1 of the year of the start date.
- If only the year is specified, and the year of first IMP dose is the same as the year of the start date, then use the date/time of first IMP dose.
- If the start date is completely unknown, then use the date/time of first IMP dose.

The following rules will be applied for partial stop dates and will be imputed for the calculation of duration of each medication:

- If only the month and year are specified, then use the last day of the month.
- If only the year is specified, then use December 31 of that year.
- If the stop date is completely unknown, do not impute the stop date. In this case the medication will be assigned to all Dosing Periods subsequent to the medication start date.

Concomitant medications will be assigned to Dosing Periods, based on the time when the medication is taken. Assignment to Dosing Periods will be done after missing dates have been imputed as described above. Concomitant medications will be assigned to a treatment based on the treatment received in the Dosing Periods as follows:

- Dosing Period 1: the start or end date is on or after IMP administration in Dosing Period 1 and prior to IMP administration in Dosing Period 2
- Dosing Period 2: the start or end date is on or after IMP administration in Dosing Period 2.

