A glossary of AE terms including reported term, SOC and PT will also be presented. [All]

Imputed dates will not be shown in the listings; all dates will be displayed as reported in the database.

The following rules will be applied for partial start dates and time:

- If only the month and year are specified and the month and year of the first dose of IMP is not the same as the month and year of the start date, then use the 1st of the month, or the date of Screening if this is later (if the latter imputation results in an end date that is earlier than the start date, then use the 1st of the month). If time is missing this will be imputed as 00:00 h
- If only the month and year are specified and the month and year of the first dose of IMP is the same as the month and year of the start date, then use the date of the first dose of IMP. If this results in an imputed start date that is after the specified end date, then use the 1st of the month, or the date of Screening if this is later (if the latter imputation results in an end date that is earlier than the start date, then use the 1st of the month). If the imputed date is the date of dosing then time will be imputed as the start time of the dosing (i.e., event will be regarded as treatment-emergent)
- If only the year is specified, and the year of the first dose of IMP is not the same as the year of the start date then January 01 will be used. If time is missing this will be imputed as 00:00 h
- If only the year is specified, and the year of the first dose of IMP is the same as the year of the start date, then the date of the first dose of IMP will be used. If this results in an imputed start date that is after the specified end date, then January 01, or the date of Screening if this is later will be used (if the latter imputation results in an end date that is earlier than the start date, then January 01 will be used). If the imputed date is the date of first dose of IMP then time will be imputed as the start time of the study medication intake (i.e., event will be regarded as treatment-emergent)
- If the start date is completely unknown, then use the date of dosing. If this results in an imputed start date that is after the specified end date, then use January 01 of the year of the end date, or the date of Screening if this is later.

The following rules will be applied for partial end/stop dates:

- If only the month and year are specified, then use the last day of the month

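### Two date rules in SAP 6.7 misfile a few medication records: a drug stopped before dosing can become concomitant with zero or negative duration, and a drug spanning both periods can lose its Period 1 assignment

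*SAP*

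**What the plan says.** SAP 6.7 derives medication dates, flags and period assignments in this order.

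- **Start imputation.** "If the start date is completely unknown, then use the date/time of first IMP dose". The same value is used in two partial cases. In one, the start is known to the month and matches the first dose: "If only the month and year are specified and the month and year of first IMP dose is the same as the month and year". In the other, it is known only to the year and matches: "If only the year is specified, and the year of first IMP dose is the same as the year of the start date". A partial start in a different month or year goes to the 1st of the month or to 1 January.
- **Stop imputation.** A month-only stop goes to the last day of the month and a year-only stop to 31 December. A completely unknown stop is left missing, and the drug is assigned to all later Dosing Periods.
- **Classification.** "the classification of medications as prior or concomitant will be performed after imputation of dates as described below". A drug taken before study medication is prior. "Medication not stopped before the date of study medication administration will be classified as 'concomitant medication". A further sentence makes any drug concomitant if its start lies between the first dosing date and the last visit; it does not mention the stop date.
- **Duration.** Stop minus start plus 1, in days.
- **Period assignment.** The lead-in says that assignment follows when the drug was taken. The bullet for the first period reads "Dosing Period 1: the start or end date is on or after IMP administration in Dosing Period 1 and prior to IMP administration in Dosing", where the closing words name the second period. The Period 2 bullet needs a start or end date on or after IMP in Dosing Period 2.

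The assigned formulation is one column of the by-participant listing. The summary tables are by treatment sequence and overall.

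For adverse events with partial start dates, SAP 4.5.2 adds a check that 6.7 lacks: "If this results in an imputed start date that is after the specified end date, then use the 1st of the month".

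**The concern.** Each rule can contradict dates that are in the database. The first can place a start after a known stop. The second tests whether a boundary date falls inside a window, when the stated aim is to capture drugs taken during that window.

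The listing and the prior and concomitant tables show a reader what else participants took. Protocol 6.5.2 prohibits nearly all medication from 14 days before first dosing until the Safety Follow-Up visit, and taking a prohibited drug is a withdrawal criterion in Protocol 7.2. Paracetamol is allowed, but not on the in-clinic days (Protocol 6.5.1). If it was stopped before check-in and its start was recorded only as the month of dosing, it would be imputed to start on Day 1, when it is barred. Compliant use would then carry a concomitant flag and a Period 1 formulation.

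**Working it through.** The plan states no figure on this point, so the check applies the rules literally to test records.

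**Notation.** D1 is the date of first IMP in Dosing Period 1 and D2 that in Dosing Period 2. The last Period 1 dose is on Day 3, which is D1+2. The wash-out is 6 to 10 days (Protocol 4.1, SAP 4.1.1.2). D2 therefore runs from D1+2+6 = D1+8 to D1+2+10 = D1+12.

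**Rules as coded**

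- Prior: start < D1.
- Concomitant: stop ≥ D1, or no stop, or D1 ≤ start ≤ last visit.
- Duration = stop - start + 1.
- Period 1: D1 ≤ start < D2, or D1 ≤ stop < D2.
- Period 2: start ≥ D2, or stop ≥ D2.
- Unknown stop: all periods after the start.

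**Rule 1: start unknown, or partial in the first-dose month or year, with a known stop k days before first dosing.** The start becomes D1, so duration = (D1 - k) - D1 + 1 = 1 - k.

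| Start as recorded | Stop | Duration (days) | Prior | Concomitant | Period assigned |
|---|---|---|---|---|---|
| Unknown | D1-1 | 0 | no | yes | 1 |
| Unknown | D1-2 | -1 | no | yes | 1 |
| Unknown | D1-10 | -9 | no | yes | 1 |
| Unknown | D1-15 | -14 | no | yes | 1 |
| Month of first dose | D1-10 | -9 | no | yes | 1 |
| Year of first dose | D1-30 | -29 | no | yes | 1 |

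Every one of these should be prior only, with no Dosing Period.

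Unaffected case, taking 20 February 2024 as an assumed D1: start recorded as January 2024, stop 5 February. The start becomes 1 January, duration is 31 + 5 = 36 days, and the drug is correctly prior only.

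**Rule 2: period assignment.** The results are the same with D2 at D1+8 and at D1+12.

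| Start | Stop | Period 1 | Period 2 | Correct? |
|---|---|---|---|---|
| D1-5 | D2-1 | yes | no | yes |
| D1-5 | D2 | **no** | yes | no |
| D1-5 | D2+1 | **no** | yes | no |
| D1-5 | unknown | yes | yes | yes |
| D1 | D2+1 | yes | yes | yes |
| D1+1 | D2+1 | yes | yes | yes |

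Failure needs a start before D1 together with a stop on or after D2. An imputed stop can produce this. With D1 = 20 February 2024 and the 6-day wash-out, D2 is 28 February. A drug started on 15 February with its stop recorded only as February 2024 gets a stop of 29 February = D2+1, and so Period 2 only. A completely unknown stop gives the better answer, both periods.

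**After the fix, same assumed D1.**

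- Unknown start, stop 10 February: start 1 January, duration 31 + 10 = 41 days.
- Month-only start, stop 10 February: start 1 February, duration 10 days.
- Year-only start, stop 21 January: start 1 January, duration 21 days.

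All three are prior only with no Dosing Period. Under an overlap rule, the two failing spanning records are assigned to both periods.

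**The case against.** The strongest reply is that the wording, read for its purpose, already gives the right answer. SAP 6.7 opens by calling any drug taken before dosing prior. Its first definition of concomitant excludes a drug stopped before dosing. The lead-in to the period bullets assigns by time of intake, so a programmer could code overlap. This shows what was intended, but it does not remove the fault. "the classification of medications as prior or concomitant will be performed after imputation of dates", and the start-based definition then makes the drug concomitant whatever its stop date. The period bullets are the only operational rule for a drug with a stop date, and they name boundary dates.

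The reply is right about the limits, and several stronger readings should be set aside.

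- A reader might infer that every record with an incomplete start and a stop before dosing is misclassified, or that every drug spanning both periods drops out of Period 1. The unaffected cases in the working show otherwise.
- A reader might infer a false difference between formulations in the reported results. No medication summary by formulation is planned. The formulation error is confined to one listing column.
- A reader might infer that exposure is hidden. The listing also prints start and stop dates, and a negative duration is visible.
- A reader might infer damage to deviation review or to the primary analysis. Nothing links the review in Protocol 9.5, the exclusion rules in SAP 3.4 or the mixed model in SAP 4.2.2 to these derived flags.

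**Conclusion.** Wrong as written, and minor. Both faults follow from the literal text of SAP 6.7.

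- **Rule 1** affects records whose start is completely unknown, or partial and matching the month (or, if year-only, the year) of first IMP, and whose stop is known and before first IMP. The duration is 0 for a stop the day before dosing and negative for anything earlier. The record moves from the prior to the concomitant summary and gains a Period 1 formulation in the listing.
- **Rule 2** affects records with a start before the first Period 1 dose and a known or imputed stop on or after the first Period 2 dose. Only the assigned-formulation column is wrong.

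The documents give no count of such records. Few are expected in healthy participants under the medication restrictions. The conclusion assumes that the rules are programmed as worded.

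**What to change.** Make three changes to SAP 6.7.

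1. Add a start-after-stop check modelled on SAP 4.5.2. If the imputed start falls after the stop date, use the 1st of the month, or 1 January of the stop year if the month is unknown. The Screening-date floor in the adverse event rule is not needed, because medication history reaches back before Screening: exclusion criterion 9 in Protocol 5.2 covers 2 months.
2. State that any drug with a stop date before first IMP is prior only.
3. Replace the period bullets with an overlap rule. Assign Dosing Period 1 if the start is before the first Period 2 dose and the stop is on or after the first Period 1 dose, or the drug is ongoing. Assign Dosing Period 2 if the stop is on or after the first Period 2 dose, or the drug is ongoing.

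The cost is a few sentences and a small programming change. No new data are needed, and no other analysis changes.
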